# 8.2. Setting

Ever treated with OAC and never treated with OAC patients will be selected from 01JAN2013-31DEC2016. To ensure access to the patients' complete medical history, they will be required to have continuous health plan enrollment for the 12 months before the first AF diagnosis date/index date (baseline period). Patient data will be assessed from index date until the earliest of death, health plan disenrollment, treatment switch (treated patients), discontinuation (treated patients), or 31DEC2016 (end of study).

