# 8.2.3. Cohorts

Patients eligible according to the above criteria will be assigned to the following cohorts:

Do not distribute for purposes outside of specific activities related to development of FDAMAs114 compliant pieces. Content within this protocol is subject to change based on communication planning and input by external review committees.

Apixaban NON-INTERVENTIONAL STUDY PROTOCOL

- 1) Ever-Treated Cohort: NVAF Patients had ≥1 pharmacy claim for apixaban, dabigatran, edoxaban, rivaroxaban, or warfarin from 01JAN2013-31DEC2016 on or after the first AF diagnosis
  - a. Apixaban cohort: Patients who initiated with apixaban on or after index date
  - b. Dabigatran cohort: Patients who initiated with dabigatran on or after index date
  - c. **Edoxaban cohort:** Patients who initiated with edoxaban on or after index date. Given the small sample size, edoxaban patients will not be included in the secondary clinical and healthcare utilization and costs analyses.
  - d. Rivaroxaban cohort: Patients who initiated with rivaroxaban on or after index date
  - e. Warfarin cohort: Patients who initiated with warfarin on or after index date
- 2) Never-Treated Cohort: NVAF patients with no pharmacy claim for an OAC from 01JAN2013-31DEC2016

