#### Apixaban

Table 2. Clinical and Treatment Pattern Outcome Variables					
Variable	Role	Operational Definition			
Stroke/SE	Outcome	Stroke/SE will be identified using hospital claims with a stroke/SE diagnosis code as the first listed ICD-9-CM or ICD-10-CM code. Stroke/SE will be classified into 3 categories: ischemic stroke, hemorrhage stroke, and SE. Time to stroke/SE will be defined as the number of days from index date to the occurrence of the first stroke/SE requiring hospitalization.			
Major bleeding	Outcome	Major bleeding will be identified using hospital claims with a bleeding diagnosis code as the first listed ICD-9-C or ICD-10-CM diagnosis or procedure code.  Time to major bleeding will be defined as the number of days from index date to the occurrence of the first major bleeding event requiring hospitalization. Major bleeding may be further stratified by gastrointestinal and intracranial hemorrhages and other major bleeding.			
Death	Outcome	Death information from the database will be used. Time to death will be defined as the number of days from index date to death.			
Discontinuation (Treated Patients)	Outcome	Treated patients will be considered to have discontinued if there was no additional refill for the index anticoagulant after 30 days of the previous prescription's run-out date.  The discontinuation date will be defined as the run-out date plus 30 days.			
Time to discontinuation (Treated Patients)	Outcome	Time to discontinuation will be defined as the number of days from the OAC prescription index date to the discontinuation date.			
Switch among anticoagulants (Treated Patients)	Outcome	A switch among anticoagulants will be defined as a prescription filled for non-index anticoagulants within 30 days before or after the run-out date.  Time to switch will be defined as the number of days from the OAC prescription index date to the first prescription date of the switch.			
Time-to-switch (Treated Patients)	Outcome	Time to switch will be defined as the number of days from the OAC prescription index date to the switch date.			

Table 2, Clinic	cal and Treatment Patt	ern Outcome Variables
	cal and frequencine i acc	

Do not distribute for purposes outside of specific activities related to development of FDAMAs114 compliant pieces. Content within this protocol is subject to change based on communication planning and input by external review committees.

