# Time-Varying Cox Regression Models (Secondary Clinical Objectives)

Time-varying Cox models will be used to compare the time to stroke/SE, major bleeding, and death between: 1) treated vs untreated; 2) each OAC vs untreated after inverse probability treatment weighting. Treatment will be used as a time varying covariate, in order to account for the untreated period of an ever-treated patient. Weights generated using IPW will be incorporated.

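### With supplies longer than 30 days, the switch window in Table 2 misses or late-dates early switches, so time on a second anticoagulant is credited to the first in the drug-specific contrasts

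*Protocol*

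**What the plan says.** Section 8.3, Table 2 of the protocol defines a switch as "a prescription filled for non-index anticoagulants within 30 days before or after the run-out date". It dates the switch as follows: "Time to switch will be defined as the number of days from the OAC prescription index date to the first prescription date of the switch".

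Discontinuation, in the same table, looks only at the index drug: "no additional refill for the index anticoagulant after 30 days of the previous prescription's run-out date". Its date is also fixed: "The discontinuation date will be defined as the run-out date plus 30 days".

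Section 8.2 ends follow-up at the earliest of several events. The only drug-related ones are "treatment switch (treated patients), discontinuation (treated patients").

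Section 8.2.3 assigns the drug cohorts by the drug started, for example "Patients who initiated with apixaban on or after index date". Section 8.7 then compares "each OAC vs untreated after inverse probability treatment weighting" for stroke/SE, major bleeding and death, and makes the same drug-by-drug comparison for costs. It gives the purpose of time-varying treatment as handling the untreated time of ever-treated patients. It does not mention moves from one anticoagulant to another.

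**The concern.** The window is anchored on run-out and reaches back only 30 days. If the supply is longer than that, a patient can fill a different anticoagulant while the window is still closed. Under Table 2 that fill is not a switch. It is not a discontinuation either, because discontinuation considers only refills of the index drug. No other stated rule ends exposure to the first drug.

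The patient therefore stays in the first drug's cohort, and under observation, while supplied with the second. In four of the five comparisons listed for secondary objectives 2 to 5 (each of apixaban, dabigatran, rivaroxaban and warfarin versus untreated), first events, person-time and costs from that stretch are credited to the wrong drug. Time-to-switch is itself a listed outcome in Table 2 and is wrong for the same patients.

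**Working it through.** The protocol gives no figure to reproduce here, so the check applies its date rules day by day.

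**Inputs from the protocol**
- Switch window: run-out minus 30 to run-out plus 30 days (Table 2).
- Switch date: the first fill that qualifies (Table 2).
- If no fill qualifies: discontinuation at run-out plus 30 days (Table 2), which ends follow-up (Section 8.2).

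**Assumptions (the protocol gives no days' supply)**
- Index-drug supply D = 30, 60 or 90 days, filled on day 0.
- The new drug is first filled on day s (1 to D), then refilled on time every 30, 60 or 90 days.
- The index drug is not refilled after the change.

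**Rule.** The switch is caught on time if D − 30 ≤ s ≤ D + 30. Otherwise it is dated at the first later new-drug fill inside that window. If there is none, follow-up ends at D + 30.

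**One window, at the run-out of this fill (a first fill, or only the last run-out counts)**

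| Index supply | First new-drug fills outside window | New drug every 30 days | Every 60 days | Every 90 days |
|---|---|---|---|---|
| 30 days | none | 0 | 0 | 0 |
| 60 days | days 1–29 (29/60 = 48%) | all dated 30 days late | all dated 60 days late | all missed; mean 75 days |
| 90 days | days 1–59 (59/90 = 66%) | all dated late; mean 44.7, maximum 60 | all dated 60 days late | 30 dated 90 days late, 29 missed; mean 82.6, maximum 90 |

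The 90-day row in detail (window days 60 to 120):
- 30-day refills: s = 1–29 are dated 60 days late and s = 30–59 are dated 30 days late. Mean = (29 × 60 + 30 × 30)/59 = 2640/59 = 44.7.
- 90-day refills: for s = 1–30 the next fill is on days 91–120, inside the window and 90 days late. For s = 31–59 the next fill is on days 121–149, outside the window, so follow-up ends on day 120, which is 89 down to 61 days after the change. Mean = (30 × 90 + 29 × 75)/59 = 4875/59 = 82.6.

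Example: a 90-day index fill on day 0 and a 90-day fill of the new drug on day 40. The next new-drug fill is on day 130, outside the window. No switch is recorded, follow-up ends on day 120, and 120 − 40 = 80 days count as the first drug.

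**A window at every run-out, second and later fills collected on time.** The previous run-out falls at the start of the current fill, so its window covers about the first 30 days.
- 60-day supply: no gap remains.
- 90-day supply: about days 31–59 remain outside, 29/90 = 32%.

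**Does a planned sensitivity analysis cover this?** Section 8.8 has an allowable-gap analysis, for example 14 days, for drug exposure. It states no change to the lower bound of the switch window. If the 14 days also narrowed that window, days 1–75 of a 90-day supply (75/90 = 83%) would fall outside it.

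**The case against.** The strongest reply is that the protocol never mentions a 90-day supply and gives neither the supply mix nor the early-switch rate. If nearly all fills cover 30 days or less, the problem vanishes. This stands: the flaw in the rule is certain, but its effect in these data is not known.

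A reader might infer more than the text supports in four ways:
- **Two thirds of every 90-day supply is blind to switching.** That share holds for a first fill, or if only the last run-out counts. Table 2 does not say to which run-out the window attaches. If it applies at each one, later fills have a gap of about one third.
- **Dating can be far more than 90 days late.** A change on day 15 of a 90-day supply with no new-drug fill from day 60 to day 120 would leave 120 − 15 = 105 days. That requires a lapse in refilling, so part of the time is probably not on the new drug. With on-time refills the maximum is 90 days.
- **The error is informative because early switches follow bleeding or intolerance.** The protocol does not say so. A first major bleed that prompts a switch occurred on the first drug and is correctly credited to it.
- **The main results are compromised.** The primary objective classifies by drug started and is untouched. In pooled treated versus untreated, the patient is on an anticoagulant either way up to run-out plus 30 days. After that, a missed switcher is either censored while still treated (Section 8.2) or, if time off the index drug counts as untreated as the abstract suggests, misclassified. Section 8.7 also makes the secondary objectives optional.

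Table 2 supports its window with a registry report on dabigatran persistence, which is not available here. Whatever that report says, it does not change how the window acts together with the censoring rule of Section 8.2.

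**Conclusion.** The point holds within limits. As written, Table 2 and Section 8.2 leave a stretch of any supply longer than 30 days in which a change of anticoagulant is not recognised. Under the assumed 90-day supply this is days 1–59 of a first fill, or about days 31–59 of later fills if a window applies at each run-out. With on-time refills, the time credited to the wrong drug is at most 60 days per affected patient when the new drug is filled every 30 or 60 days, and at most 90 days when it is filled every 90 days.

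The reach is the four drug-specific contrasts for clinical and cost outcomes, plus time-to-switch. The protocol does not allow the size or direction of bias in any hazard ratio or cost ratio to be determined. The change is worth making because it is cheap and removes the problem for every supply length, not because a large bias has been shown.

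**What to change.** In Table 2, define a switch as the earliest claim for a non-index anticoagulant after the first anticoagulant claim and on or before the index-drug discontinuation date (run-out plus 30 days), however far that claim lies from run-out. Use the claim date as the switch date, and as the censoring date under Section 8.2 in the drug-specific contrasts. The upper limit stays, so a switch is still distinguished from stopping and restarting later. Under this rule the days credited to the wrong drug in the working above fall to 0 for every supply length.

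The cost is one line in Table 2 and a small programming change, using pharmacy claims already held. The downside is that some overlapping fills, by patients who then return to the index drug, will count as switches and end follow-up early. A sensitivity analysis with the present 30-day window would show how much that matters. Tabulating days' supply for the index drugs would show how many patients the change can affect.

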#### Apixaban

1	
NON-INTERVENTIONAL	L STUDY PROTOCOL

Table 3. Health Care Resource Utilization and Cost Outcome Variables				
Variable	Role	Operational Definition		
Follow-up stroke/SE- related hospitalization costs	Outcome	Follow-up stroke/SE-related medical costs will include the first stroke/SE hospitalization costs. Costs will be adjusted as indicated above.		
Follow-up major bleeding-related hospitalization costs	Outcome	Follow-up major bleeding-related medical costs will include the first major bleeding hospitalization costs. Costs will be adjusted as indicated above.		
Follow-up all-cause health care costs	Outcome	All-cause health care costs in the follow-up period will be computed for inpatient, office, ER, total outpatient (office, ER, and other outpatient), pharmacy, and other (DME, SNF, HHA, and hospice) costs. Costs will also be adjusted to 2016 US dollars using the medical care component of the CPI. Total medical (inpatient, outpatient, and other) and total health care (medical and pharmacy) costs will be calculated PPPM.		

# 8.4. Data Sources

#### Medicare Inpatient Data

The inpatient claim file contains final action claims data submitted by inpatient hospital providers for facility cost reimbursement. Information therein includes ICD-9-CM diagnosis and ICD-9 procedure codes, ICD-10-CM diagnosis and ICD-10 procedure codes, Diagnosis Related Groups, dates of service, reimbursement amounts, hospital providers, and beneficiary demographic information. All file observations are at the claim level.

#### Medicare Outpatient Data

The outpatient claim file contains final action claims data submitted by institutional outpatient providers. Examples of such providers include hospital outpatient departments, rural health clinics, renal dialysis facilities, outpatient rehabilitation facilities, comprehensive outpatient rehabilitation facilities, and community mental health centers. File information includes diagnosis and procedure codes (ICD-9-CM diagnosis and ICD-9 procedure codes, ICD-10-CM and ICD-10 procedure codes, CMS Healthcare Common Procedure Coding System [HCPCS] codes), dates of service, reimbursement amounts, outpatient provider numbers, revenue center codes, and beneficiary demographic information. All file observations are at the claim level.

Pfizer Confidential

Page 24 of 37

Do not distribute for purposes outside of specific activities related to development of FDAMAs114 compliant pieces. Content within this protocol is subject to change based on communication planning and input by external review committees.

Apixaban NON-INTERVENTIONAL STUDY PROTOCOL

# Medicare Carrier File

The Carrier file (also known as the Physician/Supplier Part B claims file) contains final action FFS claims submitted on a CMS-1500 claim form. Most claims are from non-institutional providers such as physicians, physician assistants, clinical social workers, and nurse practitioners. The Carrier file also contains claims for other providers such as free-standing facilities. Examples include independent clinical laboratories, ambulance providers, and free-standing ambulatory surgical centers. This file also includes diagnosis and procedure codes, dates of service, reimbursement amounts, provider numbers, and patient demographic information.

# Medicare PDE Data

The Medicare PDE data contains prescription drug costs and payment data that enable CMS to make payments to the plans and otherwise administer Part D benefits. When a beneficiary fills a prescription under Medicare Part D, a prescription drug plan sponsor must submit a summary record to CMS. Unlike individual drug claim transactions, the PDE data are summary extracts using CMS-defined standard fields.

# Skilled Nursing Facility

The SNF file contains final action FFS claims data submitted by SNF providers. This file includes ICD-9-CM and ICD-10-CM diagnosis and procedure codes, dates of service, reimbursement amount, SNF provider number, and beneficiary demographic information.

# Home Health Agency

The HHA file contains final action FFS claims submitted by HHA providers. It includes number of visits, type of visit (skilled nursing care, home health aides, physical therapy, speech therapy, occupational therapy, or medical social services), diagnosis (ICD-9-CM and ICD-10-CM diagnoses), date of visits, reimbursement amount, HHA provider number, and beneficiary demographic information.

# Hospice

The Hospice file contains final action claims submitted by hospice providers. Once a beneficiary elects a hospice, all hospice-related claims are included in this file regardless of whether the beneficiary is in a Medicare FFS or Medicare managed-care plan. This file also includes level of hospice care received (eg, routine home care, inpatient respite care), terminal

Do not distribute for purposes outside of specific activities related to development of FDAMAs114 compliant pieces. Content within this protocol is subject to change based on communication planning and input by external review committees.

Apixaban NON-INTERVENTIONAL STUDY PROTOCOL

diagnosis (ICD-9-CM and ICD-10-CM diagnoses), dates of service, reimbursement amounts, hospice provider number, and beneficiary demographic information.

# Durable Medical Equipment

The DME file contains final action FFS claims submitted by DME suppliers. This file includes diagnosis (ICD-9-CM and ICD-10-CM diagnoses), services provided (CMS HCPCS codes), dates of service, reimbursement amounts, DME provider numbers, and beneficiary demographic information.

# Medicare Denominator File

The denominator file contains yearly demographic and enrollment information for enrolled or entitled Medicare beneficiaries. The file combines information from administrative enrollment records regarding Medicare beneficiary entitlement status with third-party payer information and group health plan enrollment information. It is an abbreviated version of selected data elements of the enrollment database.

Some information therein includes the beneficiary's unique identifiers, state and county codes, ZIP codes, dates of birth, dates of death, sex, race/ethnicity, age, monthly entitlement indicators (A/B/Both), reasons for entitlement, state buy-in indicators, and monthly managed-care indicators (Yes/No).

Data are collected on an ongoing basis, with the files updated annually. The file does not contain data for all beneficiaries ever entitled to Medicare, only beneficiaries entitled during the year of the data. These data are available every May for the previous year.

All patient identifiers in the database have been fully encrypted, and the database is fully compliant with the Health Insurance Portability and Accountability Act (HIPAA) of 1996.

# 8.5. Sample Size

Since the primary objectives are to evaluate the predictors of NVAF treatments, power calculation was conducted for the secondary objectives using the AVERROES (Apixaban Versus Acetylsalicylic Acid [ASA] to Prevent Stroke in Atrial Fibrillation Patients Who Have Failed or Are Unsuitable for Vitamin K Antagonist Treatment) trial.

Using the AVERROES stroke/SE rates of 1.6% and 3.7% per year for apixaban and aspirin users, respectively, a Cox proportional hazards analysis of stroke/SE would need 225 patients per group with 10% loss of follow up (Table 4).

Pfizer Confidential

Page 26 of 37

Do not distribute for purposes outside of specific activities related to development of FDAMAs114 compliant pieces. Content within this protocol is subject to change based on communication planning and input by external review committees.

#### Apixaban NON-INTERVENTIONAL STUDY PROTOCOL

			, ,	ŕ	
	Stroke/SE (from AVERROES)	Follow-up Time (Maximum)	Loss of Follow up	Accrual Time	Total Estimated Sample Size (1:1 in each group)
Apixaban	3.7%		53.7% (Amin et al  )		
Untreated 1.6%	4 years	10%	4 years	450	
		15%		522	
		20%		604	
			25%		696
			30%		802

Table 4. Power Calculation (Stroke/SE)

Using the AVERROES major bleeding rates of 1.4% per year in the apixaban group and 1.2% per year in the aspirin group, a Cox proportional hazards analysis of major bleeding would need 11,837 patients per group (Table 5).

	Major Bleeding (from AVERROES)	Follow-up Time (Maximum)	Loss of Follow up	Accrual Time	Total Estimated Sample Size (1:1 in each group)
Apixaban	1.4%		53.7% (Amin et al  )		
			10%		23674
Untreated 1.2%	4 years	15%	4 years	27498	
		20%		31870	
		25%		36848	
			30%		42494

Table 5. Power Calculation (Major Bleeding)

An alpha of 0.05, power of 80%, and accrual period of 4 years were used in the calculation.

Stroke/SE and major bleeding rates have been shown to be higher using real world data (RWD) compared to randomized controlled trial (RCT) data, so the sample size estimated to achieve 80% power may be overestimated. To compute adjusted proportional HR in the PSM analysis, a robust variance estimation will be required to be used and thus, the sample size presented here may be overestimated. This uncertainty around estimating sample size requirement for a RWD study based on RCT data should be taken into account.

Do not distribute for purposes outside of specific activities related to development of FDAMAs114 compliant pieces. Content within this protocol is subject to change based on communication planning and input by external review committees.

Apixaban NON-INTERVENTIONAL STUDY PROTOCOL

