# 8. Research Methods

# 8.1. Study Design

The study will be a longitudinal retrospective cohort analysis using the US fee-for-service (FFS) Medicare database. This database contains data from inpatient departments, outpatient departments, carrier claims, reported drug events, and beneficiaries' enrollment data. The following will be determined and compared between treatment status (treated with apixaban, dabigatran, edoxaban, rivaroxaban, or warfarin and untreated with OAC): outcomes including major bleeding, stroke/SE, and death; and health care costs and resource utilization. The overall study period will be from 01JAN2012-31DEC2016. The study will designate a 12-month baseline period prior to an index identification period (01JAN2013-31DEC2016). The date of first AF diagnosis during the study period will be assigned as the index date.

Figure 1. Study Periods for Primary and High-Risk Subgroup Objectives

(for illustration purposes only, may not be proportional)

Do not distribute for purposes outside of specific activities related to development of FDAMAs114 compliant pieces. Content within this protocol is subject to change based on communication planning and input by external review committees.

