# 8.7. Data Analysis

When performing descriptive analysis of continuous data, means, medians, and standard deviations will be provided for continuous variables. When performing descriptive analysis of categorical data, numbers and percentages will be provided for dichotomous and polychotomous variables. Bivariate comparisons of baseline characteristics and outcomes measures will be provided. Appropriate tests (eg, t-test, chi-square test) will be used based on the distributions of the measures. The cumulative incidence rate for clinical outcomes (major bleeding, stroke/SE, and death) will be calculated. The incidence rate will be calculated as the number of patients who experience the event divided by the observed time at risk. An unadjusted Kaplan-Meier curve will be drawn to illustrate time-to-event. The sample size of each cohort will be evaluated before proceeding with multivariate analysis.

The secondary objectives are optional, depending on the sample sizes and results from the primary objectives. For example, given the potential differences between ever-treated and never-treated with OAC patients, should the predictors/confounders from the primary objective be considered profound for the comparisons between the cohorts, objectives 2-5 will not be conducted.

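### Tables 4 and 5 count 4 years of follow-up after a 4-year accrual, but the data window is 4 years in total, so the stated sizes give about 43–55% power, not 80%

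*Protocol*

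**What the plan says.** Protocol Section 8.5 takes event rates from a cited apixaban-versus-aspirin trial: "Using the AVERROES stroke/SE rates of 1.6% and 3.7% per year for apixaban and aspirin users, respectively". For major bleeding it uses 1.4% and 1.2% per year. It concludes that stroke/SE "would need 225 patients per group with 10% loss of follow up" (450 in total, Table 4) and that "a Cox proportional hazards analysis of major bleeding would need 11,837 patients per group" (23,674 in total, Table 5). Each table also has rows for 15%, 20%, 25% and 30% loss. Both give 4 years of accrual and 4 years of follow-up, and the follow-up column is labelled as a maximum. Below Table 5 stands: "An alpha of 0.05, power of 80%, and accrual period of 4 years were used in the calculation".

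The calendar is set elsewhere. Section 8.1: "The study will designate a 12-month baseline period prior to an index identification period (01JAN2013-31DEC2016"). Section 8.2 follows patients from the index date to the earliest of several events, the last of which are "discontinuation (treated patients), or 31DEC2016 (end of study"). The only other year in the study period, 2012, is baseline.

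Section 8.7 adds: "The secondary objectives are optional, depending on the sample sizes and results from the primary objectives".

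**The concern.** Identification and follow-up end on the same day. A patient indexed on 01JAN2013 has at most 4 years of follow-up, and one indexed in late 2016 has almost none. With uniform accrual the mean potential follow-up is about 2 years. A calculation with 4 years of accrual and 4 years of additional follow-up gives every patient between 4 and 8 years, which this data set cannot supply. The expected number of events, and so the power, would then be far below what the tables claim.

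Section 8.5 is the Protocol's only numerical guide to how large a cohort has to be, and Section 8.7 says that cohort size will be looked at before the multivariate work. A cohort near the tabulated size could be taken as adequate when it is not, and a null bleeding result could be read as coming from a well-powered comparison.

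**Working it through.** **Inputs (Section 8.5).** Alpha 0.05 (sidedness not stated; two-sided fits the tables, one-sided does not), power 80%, 1:1 allocation, accrual A = 4 years. Annual rates, used as hazards h: 0.016 and 0.037 (stroke/SE); 0.014 and 0.012 (major bleeding). Loss L = 10% to 30%.

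**Assumptions.** Exponential times, uniform accrual, and L as an annual proportion, so the loss hazard is d = −ln(1 − L); for 10%, d = 0.1054.

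**Formulas.** With λ = h + d and further follow-up F after accrual closes, the event probability in one arm is

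P = (h/λ) × {1 − [exp(−λF) − exp(−λ(A+F))]/(λA)}.

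Let p be the mean of P over the two arms; then N = D/p, where D is the number of events needed.

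- Schoenfeld: D = 4(1.960 + 0.842)²/(ln HR)². Stroke/SE: HR = 0.016/0.037 = 0.432, D = 44.7. Bleeding: HR = 0.014/0.012 = 1.167, D = 1,321.
- Freedman: D = (1.960 + 0.842)² × [(1 + HR)/(1 − HR)]², which gives 50.0 and 1,326.

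**Step 1: reproduce the tables with A = 4, F = 4.** At 10% loss, p = 0.1077 for stroke/SE, so N = 415 (Schoenfeld) or 464 (Freedman), on either side of the stated 450. For bleeding p = 0.05533, so N = 23,880 or 23,975, against 23,674. The Lakatos log-rank method (monthly steps) is closer on every row:

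| Loss | Stroke/SE stated | Lakatos 4+4 | Bleeding stated | Lakatos 4+4 |
|---|---|---|---|---|
| 10% | 450 | 452 | 23,674 | 23,797 |
| 15% | 522 | 523 | 27,498 | 27,620 |
| 20% | 604 | 605 | 31,870 | 31,989 |
| 25% | 696 | 698 | 36,848 | 36,961 |
| 30% | 802 | 803 | 42,494 | 42,599 |

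All ten entries agree within 0.6%; other time steps keep them within about 1%.

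**Step 2: try the windows that the data could support (10% loss, Lakatos).** A = 4, F = 0 (the actual calendar) gives 1,090 and 58,261. A fixed 4 years for every patient gives 600 and 31,894. Neither fits.

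**Step 3: power of the stated sizes on the actual window (A = 4, F = 0).** At 10% loss, p = 0.04457 for stroke/SE, so 450 patients yield 450 × 0.04457 = 20.1 events, against 450 × 0.1077 = 48.5 on the 4+4 reading. Schoenfeld power is Φ(√20.1 × 0.838/2 − 1.960) = 46.7%; Freedman gives 42.6%. For bleeding p = 0.02234, so 23,674 patients yield 529 events instead of 1,310, and power is Φ(√529 × 0.1542/2 − 1.960) = 42.6%. By the Lakatos method:

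| Loss | Power, stroke/SE | N needed | Power, bleeding | N needed |
|---|---|---|---|---|
| 10% | 43.6% | 1,090 | 43.1% | 58,261 |
| 15% | 46.5% | 1,168 | 46.0% | 62,482 |
| 20% | 49.4% | 1,254 | 48.8% | 67,102 |
| 25% | 52.1% | 1,348 | 51.7% | 72,173 |
| 30% | 54.9% | 1,452 | 54.4% | 77,753 |

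**Step 4: how far the formula matters.** At 10% loss, power ranges over about 42–48% for stroke/SE and 42–44% for bleeding across the three formulas and both hazard conventions (h = rate, or h = −ln(1 − rate)). With h = rate, the N needed for stroke/SE is 1,002 (Schoenfeld), 1,090 (Lakatos) or 1,122 (Freedman); the other convention gives 963 (Schoenfeld) or 1,081 (Freedman). For bleeding the range is 58,003 to 59,382. The highest power anywhere in the 15–30% rows is 60% (stroke/SE, 30% loss, Schoenfeld).

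**Step 5: Table 4 against the text.** The text gives apixaban 1.6% and aspirin 3.7%. Table 4 sets 3.7% beside apixaban and has "Untreated 1.6" (per cent) for the other arm. Table 5, in the same layout, agrees with its text. Exchanging the two hazards leaves a 1:1 size unchanged.

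**The case against.** Nobody is recruited to these numbers. The study is retrospective, draws on the 100% Medicare file (Section 8.10), and the powered comparisons are secondary and optional. The available size is fixed by the data and may be far above even the corrected figures. This stands, and it limits the harm.

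Section 8.5 itself warns that real-world event rates exceed trial rates, so the sizes may be overestimates. That works in the opposite direction to the error, but it does not address the window. Events rise roughly in proportion to the rates, so at 10% loss the rates would have to be about 2.4 times those assumed (48.5/20.1) to close the gap, and the Protocol gives no such figure. In the other direction, Section 8.2 also ends follow-up of treated patients at switch or discontinuation.

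The 8-year span follows only if the stated 4-year accrual is kept. With accrual left free, other combinations fit within about 3%, for example no accrual and about 6 years of follow-up. Every two-sided combination that fits needs about 6 years or more, so none fits 4. That the maximum follow-up was entered as time after accrual is therefore the likely explanation, not an established one.

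Four stronger readings are tempting but unsupported:
- A reader might infer that Tables 4 and 5 are a go/no-go threshold for each drug cohort. Section 8.7 sets no numeric cut-off and does not cite the tables; its one example of not proceeding concerns confounding.
- A reader might apply 43% to every row. It belongs to the 10% rows.
- A reader might project sizes from the 53.7% loss figure in both tables. It has no time unit and no size beside it, so nothing is built on it here.
- A reader might take the exchanged rates in Table 4 to mean that the analysis assumes harm. The text states the intended direction.

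**Conclusion.** Wrong as written. Keeping the stated accrual, alpha (two-sided) and power, the tables rest on about twice the calendar time that the study has. On the Protocol's own window no row of either table reaches 80%, whichever formula is used. The shortfall is largest in the 10% rows, the ones carried into the text: about 43% power, with roughly 2.2–2.5 times the stated size needed.

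These figures rest on uniform accrual, exponential times and loss as an annual proportion. The documents do not show that any cohort will be too small, because no expected cohort counts are given. The error is therefore one of stated power, with moderate practical impact. The exchange of rates in Table 4 is a separate and certain misprint.

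**What to change.** Recompute Tables 4 and 5, and the 225 and 11,837 per group in the text, with 4 years of accrual and 4 years of total observation (no follow-up after accrual closes). State the formula, the sidedness of alpha and whether loss is annual. Alternatively, keep the sizes and state the power that they deliver on this window. The sponsor's own recalculation should supply the new entries, since results differ by several per cent between formulas. Correct Table 4 so that the rates match the text. If cohort size is weighed under Section 8.7, use the corrected figures.

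The cost is two tables and two sentences. Design, eligibility and analysis do not change, and no extra data are needed; the stated requirements simply become less favourable.
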